5.7.4. Secondary Endpoints – Patient Bothered by Bruising

For each cohort, results at each rating level of the Patient Bother by Bruising Scale (see section 2.8.3) will be summarized by visit and by buttock for each subject using counts and percentages.

A listing of Patient Bother by Bruising ratings will be provided.

5.7.5. Exploratory Endpoints –

5.8. Safety Evaluation

5.8.1. Adverse Events

The following listings will be provided based on all AEs:

- Listing of deaths.
- Listing of non-fatal SAEs.
- Listing of non-serious AEs leading to discontinuation from study.

Listing of non-serious AEs leading to interruption or discontinuation of either QWO (CCH-aaes) or mitigation treatment. The following summary tables of AEs will be presented by cohort:

- TEAEs
 - Overall summary
 - By preferred term
 - By preferred term and severity
 - By frequency of SAEs
 - By frequency of most common non-SAE
- QWO-related AEs
 - Overall summary
 - By preferred term
 - By preferred term and severity
- Mitigation-related AEs
 - Overall summary
 - By preferred term
 - By preferred term and severity

The overall summary will consist of the following items:

- Total number of AEs
 - All AEs
 - Mild AEs
 - Moderate AEs
 - Severe AEs
 - Related to QWO (CCH-aaes) Only (TEAEs overall summary only)
 - Related to Mitigation Only (TEAEs overall summary only)
 - Related to both QWO (CCH-aaes) and Mitigation (TEAEs overall summary only)
- Total number of subjects with
 - At least 1 AE

- At least 1 SAE
- At least 1 severe AE
- No severe AEs but at least 1 moderate AE
- No severe/moderate AEs but at least 1 mild AE
- At least 1 AE leading to discontinuation from study
- At least 1 AE leading to interruption or discontinuation of QWO (CCH-aaes) only (TEAE overall summary only)
- At least 1 AE leading to interruption or discontinuation of Mitigation Treatment only (TEAE overall summary only)
- At least 1 AE leading to interruption or discontinuation of both QWO (CCH-aaes) and Mitigation Treatment (TEAE overall summary only)
- Total number of subjects who died (TEAEs overall summary only)

Percentages for the total number of mild, moderate, and severe AEs will be based on the total number of all AEs in the cohort.

The by frequency summaries will also include the total number of occurrences the AE preferred term was reported as well the number of subjects with at least 1 report of the AE. Most common non-SAEs are any preferred term AE that at least 5% of the subjects in any cohort report at least once.

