Disclosure Statement: This is an interventional open-label, post-marketing study to evaluate the effect of mitigation treatments on the bruising induced by QWO (CCH-aaes). The efficacy of the mitigation treatments in reducing bruising and the safety of QWO (CCH-aaes) with mitigation treatments will also be assessed.

Name of Sponsor/Company: Endo Pharmaceuticals Inc.

Name of Marketed Product: QWOTM(CCH-aaes)

Name of Active Ingredient: Collagenase clostridium histolyticum (CCH)

Number of Subjects (planned): A maximum of 75 adult female subjects will be screened in order to enroll 48 adult female subjects into 6 cohorts, such that approximately 45 evaluable subjects complete the study.

Treatment Groups and Duration:

It is intended to enroll 6 treatment cohorts of 8 subjects each. Cohort 1, will receive QWO (CCH-aaes) and no mitigation treatment. Cohorts 2-6 will receive QWO (CCH-aaes) with different mitigation treatments.

Subjects will complete the study on Day 71. The expected duration of subject participation is up to 92 days.

Data Monitoring Committee: No data monitoring committee will be used for this study.

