3.1. Objectives and Endpoints

Secondary Objectives	Secondary Endpoints
To assess the level of aesthetic improvement of cellulite after treatment of QWO (CCH-aaes) with and/or without bruising mitigation treatment.	• The proportion of subjects with an improved (+1 or better) score on the Investigator-Global Aesthetic Improvement Scale (I-GAIS) for either buttock at the Day 71 Visit compared to Baseline. The I-GAIS is a 7-level scale ranging from +3 (very much improved) to -3 (very much worse).
To assess the safety of QWO (CCH-aaes) with mitigation treatment in subjects with cellulite.	• Percentage of subjects reporting each adverse event (AE) and treatment emergent adverse event (TEAEs).
Exploratory Objective	Exploratory Endpoint

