8. SAMPLE SIZE DETERMINATIONS

The proposed sample size is approximately 48 subjects. The sample size is based on evaluation of mitigation treatment in 6 cohorts of approximately 8 subjects each. Five (5) treatment cohorts will receive mitigation treatments and 1 treatment cohort will not receive mitigation treatment.

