No Severe TEAE, but at least one Moderate TEAE	n (%)	xx (xx.x)	xx (xx.x)	 XX (XX.X)
No Severe/Moderate TEAEs, but at least one Mild TEAE	n (%)	xx (xx.x)	xx (xx.x)	 xx (xx.x)
At least one TEAE Leading to Withdrawal from Study	n (%)	xx (xx.x)	xx (xx.x)	 xx (xx.x)
At least one TEAE Leading to Interruption/Discontinuation of OWO (CCH-aaes) only	n (%)	xx (xx.x)	xx (xx.x)	 xx (xx.x)
At least one TEAE Leading Interruption/Discontinuation of Mitigation Treatment only	n (%)	xx (xx.x)	xx (xx.x)	 xx (xx.x)
At least one TEAE Leading to Interruption/Discontinuation of both QWO (CCH-aaes) and Mitigation Treatment	n (%)	xx (xx.x)	xx (xx.x)	 xx (xx.x)
Number of Subjects with TEAEs Resulting in Death	n	XX	XX	 XX

[1] Treatment emergent adverse events (TEAEs) are adverse events with a start date after the first dose of QWO (CCH-aaes). Total number of adverse events reported includes the same adverse event occurring multiple times for a subject being counted at each occurrence. Percentages were based on the overall total number of all adverse events within the cohort.

[2] Treatment emergent adverse events (TEAEs) reported as having possibly or probably related to either QWO, or mitigation treatment, or both. Missing relationships were considered as related.

Note: Safety Population includes all enrolled subjects who received at least 1 injection of QWO (CCH-aaes) with or without mitigation treatment.

Datasets (extraction): status(ddmmmyyyy), Source: ...\xxxxxx.sas

Programming note: please include columns for cohorts 1-3 on page 1, and columns for cohorts 4-6 and Overall on page 2 if it is impossible to put all columns in one page. Cohort column headers should read: "Cohort 1 No Mitigation", "Cohort 2 Compression", "Cohort 3 Cold Packs", "Cohort 4 Arnica Patches", "Cohort 5 INhance Serum", "Cohort 6 PDL Treatment".

Table 14.3.1.2 Overall Summary of QWO-Related Adverse Events Safety Population

Datasets (extraction): status(ddmmmyyyy), Source: ...\xxxxxx.sas ddmmmmyyyy:HHMM

Programming note: Use same format as Table 14.3.1.1 with QWO- Related Adverse Events only. Replace TEAE with QWO-Related AEs. Do not include rows "Related to xxx" and "At least 1 AE leading to interruption or discontinuation of xxx".

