[1] System organ class and preferred term were coded using MedDRA dictionary (Version xx.x). If multiple serious adverse events were reported within a given system organ class and/or preferred term, only one event was counted per subject.

[2] Serious adverse events (SAEs) were determined by the investigator and marked as SAE on eCRF.

[3] Occurrence is the total number of times the serious adverse event was reported in the study.

Note: Safety Population includes all enrolled subjects who received at least 1 injection of QWO (CCH-aaes) with or without mitigation treatment.

Datasets (extraction): status(ddmmmyyyy), Source: ...\xxxxxx.sas

Programming note: please include columns for cohorts 1-2 on page 1, columns for cohorts 3-4 on page 2, and columns for cohorts 5-6 on page 3. Cohort column headers should read: "Cohort 1 No Mitigation", "Cohort 2 Compression", "Cohort 3 Cold Packs", "Cohort 4 Arnica Patches", "Cohort 5 INhance Serum", "Cohort 6 PDL Treatment".
		No M	ohort 1 Nitigation N=xxx)	 Cohort 6 PDL Treatment (N=xxx)
Preferred Term [1]	System Organ Class [1]	Subjects n (%)	Occurrence [3] n	
any Most Common Non-Serious TEAE [2]		xx (xx.x)	xx (xx.x)	 xx (xx.x)
Most Frequent Preferred Term	System Organ Class	xx (xx.x)	xx (xx.x)	 xx (xx.x)
2 nd Most Frequent Preferred Term	System Organ Class	xx (xx.x)	xx (xx.x)	 xx (xx.x)
3 rd Most Frequent Preferred Term	System Organ Class	xx (xx.x)	xx (xx.x)	 XX (XX.X)

Table 14.3.5.1 Summary of Most Common (>=5%) Non-Serious Treatment-Emergent Adverse Events by Frequency Safety Population

[1] System organ class and preferred term were coded using MedDRA dictionary (Version xx.x). If multiple serious adverse events were reported within a given system organ class and/or preferred term, only one event was counted per subject.

[2] Any non-serious TEAEs (adverse events with a start date after the first dose of QWO [CCH-aaes]) reported at least 5% of subjects in any cohort at least once.

[3] Occurrence is the total number of times the non-serious TEAE was reported in the study.

Note: Safety Population includes all enrolled subjects who received at least 1 injection of QWO (CCH-aaes) with or without mitigation treatment.

Datasets (extraction): status(ddmmmyyyy), Source: ...\xxxxxx.sas ddmmmmyyyy:HHMM

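### With about 8 subjects per cohort, the 5% in-any-cohort rule for most common non-serious TEAEs excludes nothing, and no AE column pools the mitigated subjects

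*SAP*

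**What the plan says.** SAP 5.8.1 lists the AE summary tables, says they are presented by cohort, and sets the inclusion rule for one of them: "Most common non-SAEs are any preferred term AE that at least 5% of the subjects in any cohort report at least once". The matching shell, Table 14.3.5.1 in SAP 13, is titled "Summary of Most Common (>=5%) Non-Serious Treatment-Emergent Adverse Events by Frequency Safety Population", and its second footnote repeats the any-cohort rule.

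On size, SAP 8 states: "The proposed sample size is approximately 48 subjects" and "The sample size is based on evaluation of mitigation treatment in 6 cohorts of approximately 8 subjects each". It adds: "Five (5) treatment cohorts will receive mitigation treatments and 1 treatment cohort will not receive mitigation treatment".

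The safety objective in Protocol 3.1 is "To assess the safety of QWO (CCH-aaes) with mitigation treatment in subjects with cellulite"; its endpoint is the percentage of subjects with each AE and TEAE. Protocol 9.3.2.1 asks for AE summaries for each mitigation group, and SAP 5.1 and 5.8.1 follow it.

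The AE shells (Tables 14.3.1.1 to 14.3.5.1) have columns for Cohorts 1 to 6 only. Yet the programming notes under Tables 14.3.1.1, 14.3.2.1 and 14.3.3.1 ask for cohorts 1-3 on one page "and columns for cohorts 4-6 and Overall on page 2". The notes under Tables 14.3.4.1 and 14.3.5.1 name no Overall column.

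**The concern.** A 5% threshold is meant to separate recurring events from isolated ones. In a cohort of 8 it cannot, because the smallest non-zero percentage is already above it. A preferred term reported once in the whole study would stand in a table whose title says it is among the most common.

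The second part is about precision. The objective is worded for mitigation treatment collectively, but the only percentages planned have denominators of about 8. A programmer also cannot tell whether an Overall column is wanted, since notes, grids and text disagree.

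**Working it through.** **Inputs.** Six cohorts of about 8, and about 48 in total (SAP 8). Five cohorts receive mitigation and one does not (SAP 8). The threshold is at least 5% in any cohort (SAP 5.8.1). The denominator is the Safety Population: all allocated subjects with at least one QWO injection (SAP 4.1). The SAP gives no alpha, power or assumed event rate, so every event rate below is my assumption and is shown as a range.

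**Plan's own figure.** 6 × 8 = 48, which agrees with SAP 8. The mitigated group is 5 × 8 = 40.

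**Does the rule exclude anything?** One report is 1/n, and the smallest qualifying count is 5% of n rounded up.

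| n | One report | Smallest count at or above 5% |
|---|---|---|
| 7 | 14.3% | 1 |
| 8 | 12.5% | 1 |
| 10 | 10.0% | 1 |
| 20 | 5.0% | 1 |
| 21 | 4.8% | 2 |
| 40 | 2.5% | 2 |
| 48 | 2.1% | 3 |

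No plausible departure from 8 per cohort makes the rule bite.

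**How often is a rare event labelled most common?** As written, this is the chance of one or more reports in 48 subjects, 1 − (1 − p)^48. The alternatives are binomial tails. The rate p is assumed equal in all cohorts.

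| Assumed true rate | As written (1 or more of 48) | 2 or more of 40 | 3 or more of 48 |
|---|---|---|---|
| 0.5% | 21.4% | 1.7% | 0.2% |
| 1% | 38.3% | 6.1% | 1.2% |
| 2% | 62.1% | 19.0% | 7.1% |

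**Precision of cohort and pooled columns.** With no events, the exact (Clopper-Pearson) two-sided 95% upper limit is 1 − 0.025^(1/n):

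- 0 of 8: 36.9%
- 0 of 40: 8.8%
- 0 of 48: 7.4%

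The chance of seeing an event at least once is 1 − (1 − p)^n:

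| Assumed true rate | 8 subjects | 40 subjects |
|---|---|---|
| 1% | 7.7% | 33.1% |
| 2% | 14.9% | 55.4% |
| 5% | 33.7% | 87.1% |

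**Would the Overall column in the notes supply the mitigated rate?** No. Elsewhere in the SAP, Overall means all six cohorts, so it would combine the 40 mitigated subjects with the 8 in Cohort 1.

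**The case against.** The strongest case on the other side is that this is a redundant filter with a loose title and nothing more. Much of that stands.

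- A reader might infer that every adverse event is called most common. The rule governs only Table 14.3.5.1 and only non-serious TEAEs; serious events have Table 14.3.4.1.
- A reader might infer that a rate is misreported. It is not. One event in Cohort 4 would print as 1 (12.5) under that cohort's N, which is correct, and the footnote states the any-cohort basis.
- A reader might infer that Table 14.3.5.1 merely duplicates Table 14.3.2.1. The non-serious terms overlap, but Table 14.3.5.1 adds occurrence counts and orders terms by frequency.
- A reader might infer that the percentage required by the safety endpoint is never produced. The documents do not support this. The endpoint names no pooled denominator, Protocol 9.3.2.1 prescribes summaries by mitigation group, and the cohort tables deliver them. Each subject belongs to one cohort, so pooled subject counts can also be summed by hand.

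The absence of a total may be deliberate: SAP 5.3, 5.5 and 5.8.4 say by cohort and overall, while the AE text says only by cohort. The stray Overall looks like copied boilerplate, because notes under Tables 14.2.1.2 and 14.2.2 also name a column that their grids lack. That weakens it as evidence of a lost analysis, but the conflict still has to be resolved.

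There is also a fair warning about the remedy. Replacing the any-cohort rule outright with 3 or more of 48 would drop a term reported by 2 of 8 in one cohort, since 2/48 = 4.2%. Reactions specific to one mitigation would be the most exposed.

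**Conclusion.** Two limited points hold. First, at the planned cohort size the 5% rule cannot exclude any reported non-serious treatment-emergent preferred term, so the title of Table 14.3.5.1 claims a selection that does not occur. This follows from arithmetic alone and holds for any cohorts of 20 or fewer. Second, no planned output gives an AE percentage for the mitigated subjects together, although the objective is worded that way, and three programming notes contradict their grids and the text on an Overall column.

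The consequence is modest: labelling and precision are affected, and no data are lost. The gain from pooling (upper limit 8.8% instead of 36.9% with no events) assumes that 40 mitigated subjects are injected, and it describes an average over five different mitigations. For any single mitigation, 0 of 8 still leaves 36.9%.

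**What to change.** 1. Keep all cohort columns. Add a pooled column for Cohorts 2-6 (planned N = 40) to the AE tables. Add Overall (planned N = 48) to the TEAE, SAE and QWO-related tables, but not to the mitigation-related ones: Cohort 1 has no mitigation exposure and would dilute the rate (2 events give 2/40 = 5.0% but 2/48 = 4.2%).
2. Align SAP 5.1 and 5.8.1, the shell grids and the programming notes with that choice.
3. Apply the 5% most-common label to the pooled or the overall column, and state which: at least 2 of 40, or at least 3 of 48. Set the rule as a percentage of the actual N, since 2 of 41 would be 4.9%.
4. Keep the any-cohort list under a title that does not mention 5%, so that a cluster such as 2 of 8 in one cohort stays visible.

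The cost is a few lines of SAP text, two shell columns and one retitled list, with no change to conduct or data collection. A footnote should say that the pooled column averages five different mitigations and does not bound the risk of any single one.

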5.8.1.1. Adverse Event Conventions

The following conventions will be followed:

- Table by preferred term If an AE preferred term occurred multiple times within a body system for the same subject, the preferred term will only be counted once for the subject for the summary of preferred terms. If an AE body system occurred multiple times for the same subject, the body system will only be counted once for the subject for the summary of body systems. If a subject has any AE, the subject will be counted once in the summary of subjects with at least 1 AE.
- Table by preferred term and severity If an AE preferred term occurred multiple times within a body system for the same subject, only the most severe one will be used. If the most severe preferred term of an AE occurred multiple times within a body system for the same subject, only 1 will be counted. In addition, this summary will also contain the total number of subjects with at least 1 mild, 1 moderate, or 1 severe. If a subject has at least 1 severe AE, then the subject will be counted in the severe category. If the subject has no severe AEs, but at least 1 moderate AE, then the subject will be counted in the moderate category, and if the subject has no severe and no moderate AEs, but has at least 1 mild AE, then the subject will be counted in the mild category.
- Table of frequency of preferred terms Preferred terms will be ordered by their descending frequency within the treatment cohort. If 2 or more preferred terms are tied in their frequency, then the preferred terms will be ordered alphabetically.

5.8.2. Weight and BMI

Weight and BMI at baseline, Day 71/ET, and change from baseline will be summarized by treatment cohort.

5.8.3. Vital Signs

Vital signs on injection day will be summarized at baseline (pre-injection) and post-injection time points (30 minutes after injection) and change from baseline by treatment cohort. The baseline value will be based on the pre-injection measurement at each treatment session. A listing of all vital sign information will be provided.

5.8.4. Prior and Concomitant Medications and Procedures

Prior and concomitant medications will be summarized by cohort and overall using frequency counts and percentages by active ingredient within each ATC, with ATC and active ingredients ordered alphabetically. Prior and concomitant procedures (nondrug therapies) will be summarized by cohort and overall using frequency counts and percentages with name of the procedures ordered alphabetically. Multiple uses of the same medication/procedure by a subject will be counted only once.

Subject listings of medications (indicating prior and concomitant medications) and procedures (indicating prior and concomitant procedures) will be provided.

Mitigation treatments recorded as concomitant medications or concomitant procedures will be included in associated summaries and listings.

6. **DERIVED VARIABLES**

6.1. Subject Level Variables

The following variables will be determined for each subject (see Table 11).

Variable	Definition
Age Group	18 – <25 years
	25 – <35 years
	35 – 50 years
Height (cm)	If height unit is inches, then height is equal to the recorded value multiplied by
	2.54 and then rounded to 1 decimal point.
Weight (kg)	If weight unit is pounds, then weight is equal to the recorded value multiplied
	by 0.454 and then rounded to 1 decimal point.
BMI (kg/m ²)	Weight/(Height/100) ²
BMI Group	Normal Weight (<25.0 kg/m ²)
	Overweight ($\geq 25.0 \text{ kg/m}^2$)
Baseline	For Investigator Assessment of Bruising Severity Scale: Day 1 measurement.
	Otherwise: Last evaluable measurement before first QWO (CCH-aaes)
	injection on Day 1.
Date of First QWO Injection	Day 1 visit date

 Table 11:
 Subject Level Derived Dataset Variables

Variable	Definition
Difference in number of QWO injections	(number of QWO injections in left buttock) – (number of QWO injections in right buttock).
Last Date in Study	Date of last visit where subject was seen by the investigator. If subject was lost to follow-up, then last date of contact. If the subject had contact with the site after the final visit (eg, to follow-up on an AE), the last visit date will still be used as last date in the study.
Time in Study	Last Date in Study – Date of First Injection + 1

 Table 11:
 Subject Level Derived Dataset Variables (Continued)

AE=Adverse event; BMI=Body mass index

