Inclusion/exclusion criteria	Х								
Medical history/surgical history/cellulite history including previous treatments	Х								
Prior/concomitant medications/procedures (including all prior medications/procedures for cellulite)	х	Х	Х	Х	Х	Х	Х	Х	Х
Physical examination (including height)	Х								
Weight	Х								Х
Fitzpatrick skin type	X ^a								
Vital signs	Х	X ^b							
Digital photography ^c		Х	Х	Х	Х	Х	X ^d	X ^d	Х
Cohort assignment	X e								
QWO (CCH-aaes) administration		Х					Х	Х	
Subject Assessments									
Subject-Bruising Improvement Scale (S-BIS)			Х	Х	Х	Х	X d		
Patient Bother by Bruising Scale ^g				Х	Х		X d		
Investigator Assessments									
Hexsel Cellulite Severity Scale (CSS) Subsection D	X ^h								
Clinician-Reported Photonumeric Cellulite Severity Scale (CR-PCSS)	X ⁱ								
Selection and marking of dimples to be treated with both buttocks		X ^c					X ^d	X d	
Investigator Assessment of Bruising Severity Scale		Х	Х	Х	Х	Х	X d		
Investigator- Bruising Improvement Scale (I-BIS) ^j			Х	Х	Х	X	X ^d		
Investigator- Global Aesthetic Improvement Scale (I-GAIS)							X ^d	Х	Х

Table 2: Study EN3835-401 Schedule of Assessments

	Screening Period			Tre	atment Pe	eriod			Follow-Up Period
Procedures	Day -14	Day 1 (Baseline)	Day 2	Day 4	Day 7	Day 14	Day 22 (± 3d)	Day 43 (± 3d)	Day 71/ET (+7d)
Mitigation Treatment Cohorts	Aitigation Treatment Cohorts								
Compression garments			$X^{k,j}$)					
Instant cold packs to the right buttock only		X l,p							
Arnica patches (OcuMend [®]) to the right buttock only		X ^m ,	p						
INhance Post-Injection Serum with TriHex Technology [®] to the right buttock only			X ^{n,j})					
Pulse dye laser (PDL) treatment to the right buttock only			X ^{0,j})					
Injection site reactions/local tolerability in each buttock treated		Х	Х	Х	Х	Х	Х	Х	Х
Adverse events (AEs)						X q			

Table 2: Study EN3835-401 Assessments (Continued)

^a Subjects with a Fitzpatrick skin rating of I-III will be included.

^b Before injection and approximately 30 minutes after injection. Pulse and blood pressure should be collected after the subject has been sitting for 5 minutes.

^c Buttocks will be photographed before and after injection site and dimple marking on Days 1, 22, and 43. Buttocks will also be photographed during the Days 2,

4, 7, 14, and 71 visits (ET) (no dimple or injection site markings).

^d. Before injection.

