3.4.1.2. Baseline Investigator Bruising Severity Scale Rating

The Baseline Investigator Bruising Severity Scale Rating is the rating obtained for this item from the investigator's assessments on Day 1.

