3.4.1.3. Change from Baseline Investigator Bruising Severity Scale Rating

The change from baseline Investigator Bruising Severity Scale Rating will be the visit rating minus the baseline rating. A negative change in score indicates a reduction in subject bruising severity, while a positive change in score indicates an increase in subject bruising severity.

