+2	n (%)	xx (xx.x)	xx (xx.x)	 xx (xx.x)	xx (xx.x)	
+3	n (%)	xx (xx.x)	xx (xx.x)	 xx (xx.x)	xx (xx.x)	
+4	n (%)	xx (xx.x)	xx (xx.x)	 xx (xx.x)	xx (xx.x)	
	Mean	XX.X	XX.X	 XX.X	XX.X	
	SD	XX.XX	XX.XX	 XX.XX	XX.XX	

Table 14.2.3.1 Observed and Change from Baseline in Investigator Assessment of Bruising Severity, by Visit Evaluable Population

[1] Results as reported using the Investigator Assessment of Bruising Severity Scale.

[2] Percentages are based on number of subjects with non-missing assessments at an evaluation visit.

[3] Based on results recorded at the Baseline Visit (Day 1).

[4] Based on results recorded at the Day 22 Visit, before injection.

Note: By design, Cohort 1 did not receive any mitigation treatment. For Cohort 2, mitigation treatment was administered to both left and right buttocks. For Cohorts 3-6, mitigation treatment was administered to right buttock only.

Evaluable Population includes all enrolled subjects who received at least 1 injection of QWO (CCH-aaes) with or without mitigation treatment and have at least one bruising assessment after the first dose of QWO (CCH-aaes).

Endo Pharmaceuticals Inc.

		Coho	ort 1		Coho	ort 6
		No Mitigation			PDL Treatment	
Visit		(N=	xxx)		(N=	XXX)
Bruising Severity Rating [1]	Statistic [2]	Left	Right		Left	Right

Table 14.2.3.1 Observed and Change from Baseline in Investigator Assessment of Bruising Severity, by Visit Evaluable Population

Datasets (extraction): status(ddmmmyyyy),
Source: ...\xxxxxx.sas

Programming note: please include columns for cohorts 1-2 on page 1, columns for cohorts 3-4 on page 2, and columns for cohorts 5-6 on page 3. Cohort column headers should read: "Cohort 1 No Mitigation", "Cohort 2 Compression", "Cohort 3 Cold Packs", "Cohort 4 Arnica Patches", "Cohort 5 INhance Serum", "Cohort 6 PDL Treatment".

Repeat this table for Bruising Level ratings for days 4, 7, 14, and 22, and change from baseline at days 4, 7, 14 and 22. For Day 22, please include footnote [4] (i.e. display should be "Day 22 [4]" and "Change from Baseline at Day 22 [4]").

Visit		Cohort 1 No Mitigation (N=xxx)			Cohort 6 PDL Treatment (N=xxx)		
Parameter	Statistic [1]	Left	Right		Left	Right	
Day 22 [2]							
I-GAIS Rating [3] Number of Subjects Evoluated	~						
Number of Subjects Evaluated +3 (Very much improved)	n n (%)	XX XX (XX.X)	xx xx (xx.x)		xx xx (xx.x)	xx xx (xx.x)	
+2 (Much improved)	n (%)	XX (XX.X) XX (XX.X)	XX (XX.X) XX (XX.X)		xx (xx.x) xx (xx.x)	XX (XX.X) XX (XX.X)	

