Programming note: please include columns for cohorts 1-2 on page 1, columns for cohorts 3-4 on page 2, and columns for cohorts 5-6 on page 3. Cohort column headers should read: "Cohort 1 No Mitigation", "Cohort 2 Compression", "Cohort 3 Cold Packs", "Cohort 4 Arnica Patches", "Cohort 5 INhance Serum", "Cohort 6 PDL Treatment".

		Safety P	opulation	
Parameter Timepoint	Statistic	Cohort 1 No Mitigation (N=xxx)	Cohort 2 Compression (N=xxx)	 Cohort 6 PDL Treatment (N=xxx)
Body Weight (kg)				
Baseline [1]	n	XX	XX	XX
	Mean	XX.X	XX.X	 XX.X
	SD	XX.XX	XX.XX	 XX.XX
	Median	XX.X	XX.X	 XX.X
	Min	XX	XX	XX
	Max	XX	XX	XX
Day 71/ET				
Value	n	XX	XX	XX
	Mean	XX.X	XX.X	 XX.X
	SD	XX.XX	XX.XX	 XX.XX
	Median	XX.X	XX.X	 XX.X
	Min	XX	XX	XX
	Max	XX	XX	XX
Change from Baseline	n	XX	XX	XX
-	Mean	XX.X	XX.X	 XX.X
	SD	XX.XX	XX.XX	 XX.XX
	Median	XX.X	XX.X	 XX.X
	Min	XX	XX	XX
	Max	XX	XX	XX
BMI (kq/m^2)				
Baseline [1]	n	XX	XX	 XX
	Mean	XX.X	XX.X	 XX.X
	SD	XX.XX	XX.XX	 XX.XX
	Median	XX.X	XX.X	 XX.X
	Min	XX	XX	XX
	Max	XX	XX	XX

Table 14.4.1.1 Body Weight (kg) and BMI (kg/m^2) Safety Population

[1] Based on the last evaluable measurement before first QWO (CCH-aaes) injection at the Baseline Visit (Day 1). Note: BMI = Body Mass Index; ET = Early Termination.

Safety Population includes all enrolled subjects who received at least 1 injection of QWO (CCH-aaes) with or without mitigation treatment.

Datasets (extraction): status(ddmmmyyyy), Source: ...\xxxxxx.sas ddmmmmyyyy:HHMM

Table 14.4.1.1 Body Weight (kg) and BMI (kg/m^2) Safety Population

Parameter Timepoint		Cohort 1	Cohort 2	Cohort 6
	Statistic	No Mitigation	Compression	 PDL Treatment
		(N=XXX)	(N=xxx)	(N=xxx)

Programming note: please include columns for cohorts 1-3 on page 1, columns for cohorts 4-6 on page 2 if it is impossible to put all columns in one page. Repeat for BMI Day 71/ET Value and Change from Baseline. Cohort column headers should read: "Cohort 1 No Mitigation", "Cohort 2 Compression", "Cohort 3 Cold Packs", "Cohort 4 Arnica Patches", "Cohort 5 INhance Serum", "Cohort 6 PDL Treatment".

		Bareey r	opulation	
Timepoint	Statistic	Cohort 1 No Mitigation (N=xxx)	Cohort 2 Compression (N=xxx)	 Cohort 6 PDL Treatment (N=xxx)
Baseline [1]	n	XX	Xx	XX
	Mean	XX.X	XX.X	 XX.X
	SD	XX.XX	XX.XX	 XX.XX
	Median	XX.X	XX.X	 XX.X
	Min	XX	Xx	XX
	Max	XX	Xx	XX
30 Minutes After Injection				
Value	n	XX	Xx	XX
	Mean	XX.X	XX.X	 XX.X
	SD	XX.XX	XX.XX	 XX.XX
	Median	XX.X	XX.X	 XX.X
	Min	XX	Xx	XX
	Max	XX	Xx	XX
Change from Baseline	n	XX	Xx	XX

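### Could the bruising severity baseline be a rating made after the Day 1 injection?

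*SAP*

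**What the plan says.** SAP Table 11 (section 6.1) has two baseline rules. For this scale it says "For Investigator Assessment of Bruising Severity Scale: Day 1 measurement". For everything else it says "Otherwise: Last evaluable measurement before first QWO (CCH-aaes") injection. SAP 3.4.1.2 repeats the first rule: the baseline "is the rating obtained for this item from the investigator's assessments on Day 1". Footnote [3] of shell Table 14.2.3.1 reads "Based on results recorded at the Baseline Visit (Day 1"), again without a time.

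Other places do give a time. Footnote [4] of the same shell reads "Based on results recorded at the Day 22 Visit, before injection", and the weight and BMI shell reads "Based on the last evaluable measurement before first QWO (CCH-aaes) injection at the Baseline Visit (Day 1").

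SAP 3.4.1.3 defines change as visit rating minus baseline rating. SAP 5.7.2 summarizes it by mean and SD, next to the counts at each level. The protocol's primary endpoint is the distribution of observed ratings by buttock at Day 4, and the related secondary endpoint is the same distribution by visit. Protocol 9.3.1 plans counts and percentages only, with no change score for bruising.

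**The concern.** The contrast between the two rules looks deliberate. The SAP states a pre-injection time where it wants one, and this scale alone goes without. In SAP Table 2 the row "Investigator Assessment of Bruising Severity Scale" has an unmarked Day 1 cell, while its Day 22 cell carries the footnote placing the rating before injection. SAP 3.4.1.3 adds that "A negative change in score indicates a reduction in subject bruising severity", and the shell provides change levels from -4 to +4. Negative changes need a non-zero baseline, which would be odd in buttocks not yet injected.

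If some Day 1 ratings followed injection, the change rows would subtract early treatment bruising and understate what treatment caused. If the timing also differed between cohorts, the change scores for compression (Cohort 2) and control (Cohort 1), which SAP 5.7 compares, would not be on the same footing. Listing 16.2.6.1 has an assessment date but no time, so it could not settle the order of rating and injection on the same day.

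**Working it through.** **What the text supports on timing**

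1. *The unmarked Day 1 cell.* Other rows of SAP Table 2 show that a missing before-injection footnote on Day 1 is not informative.

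| Row | Day 1 cell | Later injection days | Timing on Day 1 |
|---|---|---|---|
| Bruising severity | no footnote | Day 22: before injection | not stated |
| Photography | no footnote on the cell | Days 22 and 43: before injection | before injection (SAP 2.6) |
| Dimple marking | photography footnote only | Days 22 and 43: before injection | necessarily before injection |
| I-GAIS | not rated | Day 22: before injection; Day 43: none | not applicable |

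Two procedures that certainly precede the Day 1 injection lack that footnote on Day 1. I-GAIS lacks it on Day 43, also an injection day.

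2. *The bracket in SAP 2.7.3.* The list of rating days runs from Day 1 to Day 22 and ends with a before-injection bracket. In SAP 2.7.4, 2.8.2 and 2.8.3 the same bracket can only mean Day 22, because Day 1 is not in those lists. SAP 2.7.3 names two injection days, so the bracket may cover both. This point stays open.

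3. *Use of the word baseline.* Both schedules head the column as Day 1 and baseline. SAP 2.7.5 ties baseline to the pre-treatment image, SAP 3.5.2 to the pre-dose value and SAP 5.8.3 to the pre-injection value. All point the same way.

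4. *Why there is a separate rule.* Weight, vital signs and CR-PCSS are collected at Screening, so they need a rule that picks the last value before injection. The bruising scale has no Screening rating and one scheduled Day 1 mark. Naming that rating is an ordinary shortcut.

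5. *Shell contents.* Listing 16.2.6.1 shows sample Day 1 ratings of 4 and 2. Placeholders in these shells are not reliable: Listing 16.2.6.5 shows bother ratings on Days 43 and 71, when that scale is not scheduled, and Listing 16.2.5.1 shows injections at Screening. The -4 to +4 grid and the sign convention, which also explains positive changes, are generic.

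**What a post-injection baseline would do**

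Inputs: change = visit rating - baseline rating (SAP 3.4.1.3), a 0 to 4 scale, 8 subjects per cohort. The documents give no ratings, so those below are assumed: Day 4 left = 3, right = 2.

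- Equal baseline b on both sides: changes are 3 - b and 2 - b. For b = 0, 1, 2 they are +3/+2, +2/+1 and +1/0. The right-minus-left contrast is (2 - b) - (3 - b) = -1 each time.
- Unequal baselines, left 2 and right 1: changes are +1 and +1, contrast 0. With left 4 and right 2 they are -1 and 0, contrast +1. The Day 4 contrast in observed ratings stays at -1.
- k of 8 rated after injection at b, the rest before at 0: the column mean shifts by -kb/8. For k = 2, 4, 8 this is -0.25, -0.50, -1.00 with b = 1, and -0.50, -1.00, -2.00 with b = 2.
- Cohort 2 minus Cohort 1 shifts by -(b/8)(k2 - k1). It is 0 if timing is alike in both. For k2 - k1 = 4 it is -0.50 with b = 1 and -1.00 with b = 2.
- If every baseline is a pre-injection 0, change equals the observed rating and 4 of the 9 change levels are empty.

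**Where this can reach**

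Only the change rows of Table 14.2.3.1. The Day 4 distribution, the observed ratings at other visits, I-BIS, S-BIS and the bother scale subtract nothing. The same table prints the baseline distribution, so non-zero baselines would be seen.

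**The case for a change.** The strongest reply is that intent is not a rule. If the Day 1 rating is always made before injection, the general rule in Table 11 would already select it, so the separate rule adds nothing except room for a later rating. Should a site record two Day 1 ratings, the SAP does not say which one counts. Cold packs and arnica patches are applied immediately after injection, and the serum is also first applied on Day 1, so a late rating could even follow mitigation and move the right-left contrast in change.

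Much of this is correct as far as it goes. The separate rule is redundant on the natural reading, the time is not written down, and the listing would not reveal it. But a redundant rule is not evidence of a post-injection rating, and the schedule has only one Day 1 mark for this scale. The date-only listing is also the pattern for I-GAIS, I-BIS, S-BIS and bother; vital signs carry a time because they are repeated within Day 1. Photographs taken before the Day 1 injection go to a central repository (Protocol 8.2.1), which gives some check on a non-zero baseline. Protocol 8.2 leaves detailed instructions to a Study Operations Manual that is not available here and may fix the timing.

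**Conclusion.** No change to the plan follows. The time of the Day 1 rating is left unsaid, and analysts will fill the gap sensibly by taking the single scheduled Day 1 rating as the pre-injection state, as the documents do with baseline elsewhere. A post-injection baseline is allowed by the wording but not shown by any passage.

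The size depends on assumptions. The shift in a mean change runs from 0, if all ratings precede injection and are 0, to -2.00, if all 8 subjects in a cohort are rated afterwards at 2; unequal sides could also move the right-left contrast in change. The ratings, the number of late ratings and any difference in timing between cohorts are all supposed. Even in the worst of these cases the effect stays within supplementary descriptive rows. The primary result and every observed-rating summary would be unchanged, and no test, error rate or power is involved. Writing the time into the definition would be a harmless editorial courtesy, but no conclusion of the study depends on it.
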